2.0 Background and Significance

The Connecticut Hospice, Inc., the first Hospice who served for four decades in the United States, recently received The Joint Commission 's first advanced palliative hospital certification without recommendations for improvement, embarks on a new study.

Hospice care (Johnson-Hurzeler 1998) involves managing symptoms and quality of life for patients whose life expectancy is less than six months. (Kruse 2013) A study involving 100 hospice inpatients revealed high incidence of many symptoms, including chronic pain (62% of patients), anorexia (58%), constipation (52%), nausea (37%), vomiting (24%), sleep issues (22%), and anxiety (19%). (Potter 2003) The majority of hospice patients are prescribed opioids for pain control. The typical process involves administering a certain dosage of opioids and, depending upon pain relief and side effects, the dosage (in mgs) may be adjusted accordingly in increments of 25%. Common side effects of opioid medications include constipation, nausea, sedation, respiratory depression, dependence, and death. (Bruehl 2014)

In studies to date, marijuana has shown promise as an adjunctive medication for patients who require opioids for pain management. (Karst 2009) An Australian study—POINT (Pain and Opioids in Treatment)—collected reports from 1,514 patients on the efficacy of marijuana in combination with opioids for management of pain from a diverse range of causes. (Degenhardt 2015) In general, patients reported that the combination of marijuana and opioids was more effective for pain relief than opioids alone. (Degenhardt 2015) Another study, which included 21 patients suffering from chronic pain, found increased efficacy in pain control with the addition of marijuana to opioid regimens; investigators concluded that addition of marijuana to opioid regimens may result in a lowered effective dose of opioids. (Abrams 2011) In the same study, investigators reasoned that marijuana facilitates the activities of opioids either by slowing opioid

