metabolism or by increasing plasma opioid levels. (Abrams 2011) Marijuana may also facilitate the pain-relieving effects of opioid medications by acting upon opioid receptors. (Cichewicz 2004; Abrams 2011) Animal studies have shown the possibility of direct interaction between cannabinoid and opioid receptors. (Bushlin 2010) In studies, marijuana has been shown to reduce pain associated with multiple sclerosis, HIV, chronic neuropathic pain, rheumatoid arthritis, and acute pancreatitis. (Fine 2013) Surveys of medical marijuana have shown that the drug can improve pain and control insomnia with minimal side effects in some patients. (Wilsey 2008) Marijuana is also known to help mitigate nausea and vomiting. (Sharkey 2014) Dronabinol, a pill which is chemically identical to THC, was approved in 1992 by the FDA as an appetite stimulant in AIDS patients. (Grant 2005) The latter may indicate the use of marijuana for hospice patients experiencing anorexia.

Most studies of the medical benefits of marijuana so far have included fewer than 200 patients. Federal restrictions make it difficult for the research to advance. Marijuana is currently characterized by the Federal Government as a Schedule-I controlled substance, meaning that according to federal law, "(A) The drug or other substance has a high potential for abuse. (B) The drug or other substance has no currently accepted medical use in treatment in the United States. (C) There is a lack of accepted safety for use of the drug or other substance under medical supervision." (21 U.S. Code *812) The DEA and FDA have yet to grant their approval for largescale studies of the medical applications of marijuana; however, in 2014, the FDA vowed to reexamine the scheduling of marijuana so that more large-scale research could perhaps be conducted. (Ferner 2014)

In 2012, Connecticut lawmakers passed a law allowing for the palliative use of marijuana. The law enables doctors to prescribe marijuana (i.e. dried leaves) and its derivatives (i.e. oils, waxes, edibles, transdermal, and sublingual preparations) to patients suffering from specific conditions.

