3.0 Objectives

Primary

1. Improve pain management as identified by decreased overall numeric pain scores
2. Reduce opioid dosage increases
3. Reduce overall opioid utilization

Secondary

Evaluate changes in patient weight, appetite, nausea and vomiting, O2 saturation, feelings of well-being, anxiety, and depression.

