4.0 Study Design and Methodology

Design

This will be an open-label study. Patients will choose to participate in a Marijuana adjuvant treatment group, receiving marijuana in combination with standard opioid therapy.

The goal is to enroll at least 66 Hospice patients in the study.
Methodology

Patients will be notified of the study's existence through communication with the study's investigation team at time of admission. Patients will be screened for study eligibility—see section 6.0 for study eligibility factors—and if the patient is both eligible and interested in participating, the sub-investigator will discuss and review the informed consent form with the patient and obtain their signature; the patient will then have a consultation with a prescribing physician; and, if the physician has determined that medical marijuana is a viable option for that patient, registration with the Connecticut Medical Marijuana program will begin. For patients who have already been prescribed both marijuana and opioid medication upon admission to Hospice, signing the consent form will complete study enrollment.

Patients' initial opioid dose, dosing schedule and numeric pain score will be recorded. For the duration of the study (at least five days) changes in opioid doses and numeric pain scores will be tracked daily.

Marijuana will be administered to the patient via oral route three times daily for at least five days. Patients will receive CBD:THC product provided by NIDA.

On admission to the study, a modified Edmonton Symptom assessment scale to quantify baseline appetite, depression, nausea, vomiting, overall well-being, and anxiety.

Data Tracking: Primary objective tracking will include average numeric pain scores and number of opioid dosage increases and average daily opioid amount (mg equivalents of morphine).

Secondary objectives include Weight, Appetite, N/V, O2 Saturation, Self-reported data points from the modified Edmonton Assessment Scale.

Data Tracking Intervals: Primary objective tracking of pain will be daily every 4 hours (twice per shift). Secondary objective tracking as follows: Weight daily, Appetite every 8 hours (every shift), N/V, O2 saturation as reported by clinician documentation, Edmonton scale results three times weekly.

Analysis

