Following the data collection phase, investigators will calculate average numeric pain scores, average number of increases in opioid dosage and average daily opioid amount (mg equivalents of morphine). Analysis will examine whether the addition of CBD/THC with opioid therapy had

a stabilizing effect or improvement in pain management (lower average numeric pain scores, few dosage increases, lower opioid doses and subsequently less opioid therapy needed)

Additionally calculations will include results of changes in weight, calculation of average changes in O2 saturation, and average changes in Edmonton-Scale scores for secondary data collection points.

Patient Selection to Ensure Validity

The study will enroll patients with a primary diagnosis (Table 1) of cancer and non-cancer with associated pain considered to have a terminal illness requiring end of life care, utilizing routine or as needed opioid therapy for pain.

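### Lower opioid dose is read as better pain control whatever the reason for it, and the reason is not recorded, so side-effect-driven reductions could be reported as opioid-sparing

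*Combined protocol and SAP*

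**What the plan says.** Two of the three primary objectives in Section 3.0 concern opioid quantity: "Reduce opioid dosage increases" and "Reduce overall opioid utilization". The Analysis part of Section 4.0 lists what would indicate a stabilising effect or an improvement in pain management: "lower average numeric pain scores, few dosage increases, lower opioid doses and subsequently less opioid therapy needed".

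For the primary objectives, Section 4.0 tracks "average numeric pain scores and number of opioid dosage increases and average daily opioid amount (mg equivalents of morphine"). Dose changes are followed daily. Section 10.0 repeats the same three averages. Neither section asks why a dose was lowered, held or not raised.

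Section 2.0 describes usual opioid practice: "depending upon pain relief and side effects, the dosage (in mgs) may be adjusted accordingly in increments of 25" per cent. It also states: "Common side effects of opioid medications include constipation, nausea, sedation, respiratory depression, dependence, and death". On the interaction, it reports that in a cited study "investigators reasoned that marijuana facilitates the activities of opioids either by slowing opioid" "metabolism or by increasing plasma opioid levels", and then adds a possible action at opioid receptors.

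Section 7.0 names six adverse events, all psychiatric or motor, plus a catch-all for conditions not expected from the admitting diagnosis or the usual course of the illness.

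**The concern.** By the protocol's own account of practice, a lower opioid dose has two opposite meanings. The patient may need less because pain is controlled, or the dose may have been cut or kept down because the patient was over-sedated or otherwise harmed. Both move the opioid measures in the same direction, and the plan reads that direction as improvement.

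The second meaning is foreseeable here. If adding study drug slows opioid metabolism or raises plasma levels, as the cited reasoning suggests, some patients may show opioid side effects on an unchanged opioid dose, and staff may respond by reducing it. With no comparator, no between-group contrast can show whether this happened. Section 2.0 says the study is meant to support wider legal indications, so a misread opioid result would carry weight.

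**Working it through.** The plan gives no figure on this point to reproduce. The target of 66 patients is used below only in step 5.

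**1. How each event scores under the plan as written**

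| Event | Daily morphine equivalents | Number of increases | Reading under Section 4.0 |
|---|---|---|---|
| Dose cut, pain controlled | Lower | None added | Improvement |
| Dose cut for sedation or another side effect | Lower | None added | Improvement |
| Increase not needed | Not raised | None added | Improvement |
| Increase withheld for a side effect | Not raised | None added | Improvement |

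No primary item distinguishes row 1 from row 2, or row 3 from row 4.

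**2. Could other items distinguish them?**

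- *Pain scores.* If opioid exposure rises, pain would tend to fall as well, so all three primary measures can move favourably together. Suppose plasma levels rise by one third and the dose is then cut by 25%: 0.75 × 1.333 = 1.00. Exposure is back where it started, while the milligram measure is 25% lower.
- *Modified Edmonton scale.* The items named in Sections 4.0 and 10.0 are appetite, depression, nausea and vomiting, well-being and anxiety. Nausea is covered; sedation is not.
- *Adverse events.* Section 7.0 names neither sedation nor respiratory depression. Sedation in a dying patient may be judged part of the illness and so fall outside the catch-all.
- *Oxygen saturation.* It is secondary, taken from clinician documentation with no fixed schedule, and summarised as an average change. It is not linked to opioid dose changes.

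**3. Illustrative size, daily amount.** Assume no analgesic benefit, equal baseline doses, and a fraction f of patients with one 25% cut in force for the whole averaging period. The 25% is borrowed from the increment in Section 2.0; f is assumed.

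Fall in mean daily amount = f × 25%:

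- f = 10%: 2.5%
- f = 20%: 5.0%
- f = 30%: 7.5%
- f = 40%: 10.0%

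If the cut applies for only three of five days, multiply by 3/5: the range becomes 1.5% to 6.0%.

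**4. Illustrative size, number of increases.** A cut does not by itself lower this count. One withheld increase in a fraction f of patients removes f × 1 from the mean, that is 0.10 to 0.40 increases per patient over the same range of f.

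**5. Would it look like a finding?** The plan specifies no test. For scale only, take a paired comparison with n = 66, two-sided 5%, mean fall d = 0.25f and s = √(SD² + 0.25²·f(1 − f)). Then P(nominally significant reduction) ≈ Φ(d√66/s − 1.96). At f = 20% and an assumed SD of change of 15%, 25% or 40%, this is 0.62, 0.33 or 0.16. Over f = 10% to 40% and the same SDs, it runs from 0.07 to 0.99.

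**The case against.** **The protocol does not predict toxicity.** A reader might infer that its own mechanism forecasts over-sedation. It does not. Section 2.0 reports another study's reasoning about facilitated opioid activity, sets a receptor mechanism beside it, and draws a favourable inference, a lower effective opioid dose. Toxicity comes only from combining that reasoning with the general list of opioid side effects. It is foreseeable, not predicted. This part of the objection stands.

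**There is separate safety capture.** Section 7.0 requires adverse reactions to be documented immediately and evaluated, with discontinuation of the study possible. Oxygen saturation and heart rate are examined, nurses attend dosing, and Section 13.0 provides ongoing review. So it would be wrong to say the safety signal is bound to be lost. These channels may catch some cases, but none is tied to the opioid outcomes, so they do not correct how those outcomes are read.

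**A reduction prompted by a side effect may still be real sparing.** If plasma levels rise and pain stays controlled on fewer milligrams, less opioid has in fact been used. Also, if exposure is not raised, a cut should tend to push pain scores up. Both points are fair. They argue against deleting such reductions from the primary measure, but not against showing which reductions they are.

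**The rates are assumed.** This is correct. The documents give no frequency of side-effect-driven cuts and no variability of opioid dose.

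**Missed doses in declining patients.** A reader might infer that these lower the measure in the same way. That holds only if administered amounts are counted; Section 4.0 does not say whether amounts are ordered or administered.

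**Conclusion.** The concern holds in this form: following the plan as written, opioid reductions or withheld increases made for side effects could be reported as opioid-sparing, and no item linked to the opioid outcomes would reveal it. It affects two of the three primary measures, and the third is not a dependable check.

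The size cannot be obtained from the documents. The illustration gives a 2.5% to 10% fall in mean daily opioid amount. It rests on assumed rates of 10% to 40%, one 25% cut per affected patient in force throughout, equal baseline doses and no analgesic effect; shorter duration shrinks it.

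A reader might go further and say that such cuts count as trial success, or that the error will certainly occur. The documents do not support either. The study is labelled exploratory, and has no success threshold and no specified test; the wording at issue is a reading of improvement. Whether it misleads depends on how many side-effect-driven changes occur, which the plan as it stands would not show.

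**What to change.** Data collection and reporting only; no change to clinical management.

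- **Section 4.0, data tracking.** Record a reason for every opioid decrease, held dose or missed dose, and for every increase withheld because of side effects: pain controlled; side effect (which one); unable to take; other. State whether daily morphine equivalents are ordered or administered amounts.
- **Sections 4.0 (Analysis) and 10.0.** Keep the all-cause daily opioid amount and number of increases as the primary measures, and show each broken down by reason. Report side-effect-driven reductions, as patients and as events, as a safety result beside them. Do not describe those reductions as improved pain management or as opioid-sparing.

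Benefit should not be restricted to decreases coded as pain controlled. That would filter the primary measure on an unblinded judgement made after treatment starts, with no matching rule for increases.

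The cost is one reason field on a record already kept daily, some staff instruction, and added summary rows. There are three limits. Unblinded staff assign the reason. The saving attributed to pain control may come out smaller. A fall in as-needed requests generates no order to code, so it should be shown as unclassified.

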5.0 Study Population

Adult (≥18 years of age), non-pregnant, alert and oriented hospice inpatients. Subjects must take opioids for pain management either routinely scheduled or on an as needed basis to qualify.

Inclusion / Exclusion Criteria

Included: alert adults (age 18+) requiring opioids for pain management (routine or as needed) with a cancer diagnosis or non-cancer diagnosis as their terminal illness as defined in Table 1 .

Excluded: pregnant women, children (patients < 18 years of age), minimally or unresponsive patients unable to take oral medications, and agitated combative patients.

Sample Size

66 patients is the target.

The average length of stay at The Connecticut Hospice, Inc. is twelve days. At the end of each nine day cycle (i.e. the time by which the average patient has three days to live), we can expect roughly thirty-five out of thirty-nine inpatients to take opioid medication(s) to manage pain.

Since the study will happen over about 180 days, this means the population size for the length of the study should be about 700 patients.

Therefore, assuming a 95% confidence interval, a 5% error margin, and a statistical significance level of .05, we have calculated a target sample size of 66 patients.

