6.0 Study Agent and Intervention Description

Options

Capsules: 40 mg/1 .5 mg or 80 mg/3 mg CBD:THC per capsule (Gelatin capsules: Apothecon).

Interventions

All patients and marijuana naive (no marijuana use within the last 30 days) will receive 40/1.5 mg CBD:THC three times daily. Marijuana tolerant patients (Marijuana use currently or within the last 30 days) will receive 80 mg/3 mg CBD: THC three times daily.

Patients who experience three scheduled opioid dosage increases while receiving the 40 mg/1 .5 mg regimen will have an increase to the 80 mg/3 mg dosage three times daily for the remainder of the study.

Security/Records

All study drugs will be secured abiding by federal and state regulations for storage of Scheduled substances.

Running inventory will be maintained for all study product. The pharmacy staff will record receipt and dispensing of study product, and maintain adequate supply and availability for the study population in accordance with all federal narcotic regulations.

Storage of Scheduled study product will be accessible to pharmacy personnel and clinical staff caring for the patient, in accordance with the hospital's policies and procedures and in accordance with both state and federal storage requirements.

7.0 Study Schedule:

Patients must have, at minimum, a 3-day life expectancy

SCREENING

ENROLLMENT

DOSING -5 Ongoing Assessment of Patient Progress and Safety

DATA COLLECTION

DATA ANALYSIS

Adverse/Serious Adverse Events: dysphoria, extreme anxiety/panic attack, paranoia, psychosis, ataxia, impaired motor coordination, any condition that would typically not be associated with the patients admitting diagnosis or normal course of illness.

Adverse reactions will be immediately documented on the Connecticut Hospice Adverse Drug Reaction Form and evaluated by the PI and clinical investigation team. The research team will

determine whether changes to the study protocol, including discontinuation of the study, are warranted.

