10.0 Statistical Analysis Plan

The calculation of the average daily numeric pain scores, the average number of opioid dosage increases, and average daily opioid amounts (mg of morphine equivalents) will be evaluated. In addition, the secondary measures of, oxygen saturation, heart rate and body weight, findings from the Edmonton numeric assessment scale: nausea/vomiting, appetite, depression, anxiety and overall well-being will be examined.

There will be a database for tracking all primary and secondary data.

Sample size determination

See sample-size calculation and justification under "Study Population" (section 6.0).

Missing, unused, and spurious data

Missing, unused, and spurious data will be documented ongoing and noted in the final study results.

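### The stated inputs (95% confidence, 5% margin, population of about 700) do not give 66 patients unless an unstated proportion near .05 or .95 is added, and no primary measure is a proportion

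*Combined protocol and SAP*

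**What the plan says.** The sample-size text is in section 5.0 of the combined protocol and SAP. It gives an average stay of twelve days, uses nine-day cycles, and says that at the end of each cycle "we can expect roughly thirty-five out of thirty-nine inpatients to take opioid medication(s) to manage pain". Over a study of about 180 days, "this means the population size for the length of the study should be about 700 patients". From this and a 95% confidence level it concludes, with "a 5% error margin, and a statistical significance level of .05, we have calculated a target sample size of 66 patients".

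The SAP (section 10.0) adds nothing of its own. It says "See sample-size calculation and justification under" the Study Population heading, which it numbers 6.0, although the calculation is in 5.0.

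The analysis text in section 4.0 says that "investigators will calculate average numeric pain scores, average number of increases in opioid dosage and average daily opioid amount" (in morphine equivalents). Section 10.0 lists the same three averages. Neither section states an expected proportion, SD, effect size, power or allowance for patients who cannot be evaluated.

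**The concern.** The text presents 66 as the output of a calculation, so a reader should be able to repeat it. The named inputs belong to a survey formula for one proportion, and the formula cannot be run without a value of p. The .05 significance level adds nothing, because it restates the 95% confidence.

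Supplying a p would not settle the matter. The trial estimates a mean pain score, a mean number of opioid dose increases and a mean daily morphine-equivalent dose. The precision of a mean depends on its SD, which is never mentioned.

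This is the only statistical justification for the trial's size. As written, the planned precision cannot be checked, and a reader could believe that the results will be accurate to within 5%, which nothing supports. Section 4.0 intends to judge whether the addition stabilises or improves pain management, so what 66 patients can show should be stated.

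**Working it through.** **Inputs, all from section 5.0.** z = 1.96 (95%, taken as two-sided); margin E = 0.05; N = 700; the only proportion given, 35/39 = 0.897. The population figure reproduces: 180/9 = 20 cycles, and 20 × 35 = 700.

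**Formula.** n0 = z² p(1 − p)/E², then n = n0/(1 + (n0 − 1)/N).

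| p | n0 | n with N = 700 |
|---|---|---|
| 0.5 (convention when p is unknown) | 384.16 | 248.3 |
| 35/39 | 141.44 | 117.8 |
| .05 or .95 | 72.99 | 66.2 |

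For example, at p = 0.5: 384.16/(1 + 383.16/700) = 248.3. Solved backwards, 66 needs p = .0498 or .9502. The documents give no such proportion. The .05 significance level may have been entered as p, but that is an inference.

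**Other readings.**

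- One-sided z, N = 700: 195.3 at p = 0.5, 87.3 at 35/39, 48.0 at .05 or .95.
- N/(1 + N·E²) = 700/2.75 = 254.5.
- 5% as a margin relative to a mean: n = 66 corresponds to n0 = 66 × 699/634 = 72.8, so the coefficient of variation must be √72.8 × 0.05/1.96 = 0.218. None is stated.

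**Does the population figure explain the gap?** No.

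| N | Source | p = 0.5 | 35/39 |
|---|---|---|---|
| 525 | 180/12 × 35 | 222 | 112 |
| 585 | 180/12 × 39 | 232 | 114 |
| 780 | 180/9 × 39 | 258 | 120 |
| 1,400 | 700 doubled, for the roughly one-year timeline in section 13.0 | 302 | 128 |

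For n = 66, N would have to be (n0 − 1)/(n0/66 − 1), which is about 79 at p = 0.5 or 123 at 35/39.

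**Margin that 66 gives for a proportion.** 1.96 √(p(1 − p)/66) × √(634/699):

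- p = .05 or .95: 5.0 points
- p = 35/39: 7.0 points
- p = 0.5: 11.5 points (12.1 without the correction)

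**What 66 gives for a mean within-patient change.** The half-width in SD units is t(n−1)/√n. The detectable change is for a one-sample t test on the change, two-sided .05, 80% power. Not all 66 may be evaluable: treatment is planned "three times daily for at least five days", while section 7.0 says "Patients must have, at minimum, a 3-day life expectancy". The documents give no evaluable fraction, so 70% and 50% are assumptions (0.70 × 66 ≈ 46; 0.50 × 66 = 33).

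| Evaluable | 95% half-width | Detectable at 80% power |
|---|---|---|
| 66 | 0.25 SD | 0.35 SD |
| 46 | 0.30 SD | 0.42 SD |
| 33 | 0.35 SD | 0.50 SD |

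If the SD of change were 2 to 3 pain points (assumption), the half-width would be 0.5 to 0.7 points with 66 patients and 0.6 to 0.9 with 46.

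**The case against.** The strongest reply is that the sum may have been done correctly with an undisclosed or mislabelled input. With p = .05 the formula returns 66.2, and .05 is printed in the sentence. That may well be what happened. It does not rescue the text, because .05 is offered there as a significance level and no outcome of the trial has an expected proportion of 5%.

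A second reply is that this is an exploratory pilot, open-label with a single treated group, and that its SAP names no test or decision rule, so no planned conclusion depends on the 5%. A pilot may indeed choose 66 for feasibility. But this protocol does not say so; it claims a calculation, and that claim is wrong as written.

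A third reply is that restating precision for a mean change goes beyond the plan, which speaks of averages and names no paired test. This stands as a caution:

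- Any power statement should be conditional on a paired test being used.
- The baseline needs defining. Section 4.0 says that each patient's "initial opioid dose, dosing schedule and numeric pain score will be recorded", but a single initial score would be set against an average of scores taken every four hours.
- For patients on as-needed opioids, a baseline daily total does not follow from dose and schedule.
- Some patients enter already prescribed marijuana, so their baseline may not be untreated.

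The wrong section number in the SAP is clerical and carries no weight here.

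**Conclusion.** The concern holds. From the stated confidence, margin and population, 66 is reproduced only by adding an expected proportion of about .05 or .95 that the documents do not contain. The usual default gives about 248 and the section's own 35/39 about 118. Populations from 525 to 1,400 still give 222 to 302 at p = 0.5. More fundamentally, the 5% margin refers to a kind of quantity that the trial does not have among its primary measures.

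This assumes that the wording describes the one-proportion formula. The relative-margin reading needs a coefficient of variation of about 0.22, which is equally unstated. The finding does not show that 66 is too few: about 0.25 SD of precision on a mean change may be adequate for a pilot. It shows that the stated justification does not support the number. The evaluable fractions and pain-score SDs above are assumptions used only for scale.

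**What to change.** 1. In section 5.0, keep the target of 66, delete the derivation from a 5% margin and a population of 700, and state the actual basis for the number (feasibility, if that is the case).
2. Define baseline and change for pain score and daily morphine equivalents, including how baseline is set for as-needed opioid users and for patients already taking marijuana.
3. Add a precision statement such as: *For mean within-patient change from baseline to the on-treatment average in pain score or daily morphine equivalents, 66 evaluable patients give a 95% CI half-width of about 0.25 SD and, if a paired t test is used, 80% power (two-sided .05) for a change of 0.35 SD. With 46 evaluable (70%, assumption) these become about 0.30 SD and 0.42 SD. The number of opioid dose increases will be reported as a mean with its 95% CI.*
4. Label any margin quoted for a proportion as the p = 0.5 worst case, about ±12 points at 66 without finite-population correction.
5. In section 10.0, correct the cross-reference from 6.0 to 5.0.

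The cost is one rewritten paragraph, the baseline definitions and one cross-reference, with no extra patients. The stated precision becomes less favourable and depends on how many patients are evaluable. Separately, the planned treatment period in section 4.0 and the minimum life expectancy in section 7.0 should be reconciled by the sponsor.
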